12.0 Provisions to Monitor the Data to Ensure the Safety of Subjects

12.1 Adverse Event Monitoring

Adverse event data collection and reporting, which are required as part of every clinical trial, are done to ensure the safety of Subjects enrolled in the studies as well as those who will enroll in future studies. Adverse events are reported in a routine manner at scheduled times during a trial. Additionally, certain adverse events must be reported in an expedited manner to allow for optimal monitoring of patient safety and care.

All patients experiencing an adverse event, regardless of its relationship to study drug/device, will be monitored until:

- the adverse event resolves or the symptoms or signs that constitute the adverse event return to baseline;
- any abnormal laboratory values have returned to baseline;
- there is a satisfactory explanation other than the study procedures for the changes observed; or
- death.

12.1.1 Definition of Adverse Event

An adverse event (AE) is any untoward medical occurrence in a patient receiving study treatment and which does not necessarily have a causal relationship with this treatment. An AE can therefore be any unfavorable and unintended sign (including an abnormal laboratory finding), symptom,

or disease temporally associated with the use of an experimental intervention, whether or not related to the intervention.

12.1.2 Severity of Adverse Events

The severity of an AE is graded as follows:

- Mild (grade 1): the event causes discomfort without disruption of normal daily activities.
- Moderate (grade 2): the event causes discomfort that affects normal daily activities.
- Severe (grade 3): the event makes the patient unable to perform normal daily activities or significantly affects his/her clinical status.
- Life-threatening (grade 4): the patient was at risk of death at the time of the event.
- Fatal (grade 5): the event caused death.

12.1.3 Serious Adverse Events

A “serious” adverse event is defined in regulatory terminology as any untoward medical occurrence that:

- ***Results in death.***
If death results from (progression of) the disease, the disease should be reported as event (SAE) itself.
- ***Is life-threatening.***
The patient was at risk of death at the time of the event; it does not refer to an event that hypothetically might have caused death if it were more severe.
- ***Requires in-patient hospitalization or prolongation of existing hospitalization for ≥ 24 hours.***
- ***Results in persistent or significant disability or incapacity.***
- ***Is a congenital anomaly/birth defect***
- ***Is an important medical event***

Any event that does not meet the above criteria, but that in the judgment of the investigator jeopardizes the patient, may be considered for reporting as a serious adverse event. The event may require medical or surgical intervention to prevent one of the outcomes listed in the definition of “Serious Adverse Event“.

For example: allergic bronchospasm requiring intensive treatment in an emergency room or at home; convulsions that may not result in hospitalization; development of drug abuse or drug dependency.

12.1.4 Steps to Determine If an Adverse Event Requires Expedited Reporting

Step 1: Identify the type of adverse event

Step 2: Grade the adverse event

Step 3: Determine whether the adverse event is related to the protocol therapy

Attribution categories are as follows:

- Definite – The AE *is clearly related* to the study treatment.
- Probable – The AE *is likely related* to the study treatment.
- Possible – The AE *may be related* to the study treatment.
- Unrelated – The AE *is clearly NOT related* to the study treatment.

Note: This includes all events that occur within 30 days of the last dose of protocol treatment. Any event that occurs more than 30 days after the last dose of treatment and is attributed (possibly, probably, or definitely) to the agent(s) must also be reported accordingly.

Step 4: Determine the prior experience of the adverse event.

Expected events are those that have been previously identified as resulting from administration of the agent. An adverse event is considered unexpected, for expedited reporting purposes only, when either the type of event or the severity of the event is not listed in:

- the current known adverse events listed in the Agent Information Section of this protocol;
- the current Investigator's Brochure

12.1.5 Reporting Requirements for Adverse Events

Expedited Reporting

- The Principal Investigator must be notified within 24 hours of learning of any serious adverse events, regardless of attribution, occurring during the ablation or within 30 days of the ablation.
- The IRB and FDA must be notified within 10 business days of "any unanticipated problems involving risk to subjects or others" (UPR/UPIRSO).

The following events meet the definition of UPR:

1. Any serious event (injuries, side effects, deaths or other problems), which in the opinion of the Principal Investigator was unanticipated, involved risk to subjects or others, and was possibly related to the research procedures.
2. Any serious accidental or unintentional change to the IRB-approved protocol that alters the level of risk.
3. Any deviation from the protocol taken without prior IRB review to eliminate apparent immediate hazard to a research subject.

4. Any new information (e.g., publication, safety monitoring report, updated sponsor safety report), interim result or other finding that indicates an unexpected change to the risk/benefit ratio for the research.
5. Any breach in confidentiality that may involve risk to the subject or others.
6. Any complaint of a subject that indicates an unanticipated risk or that cannot be resolved by the Principal Investigator.

Routine Reporting

- All other adverse events - such as those that are expected, or are unlikely or definitely not related to the study participation - are to be reported annually as part of regular data submission.

12.2 Adherence to the Protocol

Except for an emergency situation in which proper care for the protection, safety, and well-being of the study patient requires alternative treatment, the study shall be conducted exactly as described in the approved protocol.

Emergency Modifications

Investigators may implement a deviation from, or a change of, the protocol to eliminate an immediate hazard(s) to trial subjects without prior IRB approval.

For any such emergency modification implemented, the IRB must be notified within five (5) business days of making the change.

Other Protocol Deviations/Violations

All other planned deviations from the protocol must have prior approval by the Principal Investigator and the IRB. According to the IRB, a protocol deviation is any unplanned variance from an IRB approved protocol that:

- Is generally noted or recognized after it occurs
- Has no substantive effect on the risks to research participants
- Has no substantive effect on the scientific integrity of the research plan or the value of the data collected
- Did not result from willful or knowing misconduct on the part of the investigator(s).

Personnel will report to any sponsor or data and safety monitoring committee in accordance with their policies. Deviations should be summarized and reported to the IRB at the time of continuing review.

An unplanned protocol variance is considered a violation if the variance:

- Has harmed or increased the risk of harm to one or more research participants.
- Has damaged the scientific integrity of the data collected for the study.
- Results from willful or knowing misconduct on the part of the investigator(s).

- Demonstrates serious or continuing noncompliance with federal regulations, State laws, or University policies.

Study personnel should report protocol violations within one (1) week of the investigator becoming aware of the event using the same IRB online mechanism used to report Unanticipated Problems.

12.3 Amendments to the Protocol

Should amendments to the protocol be required, the amendments will be originated and documented by the Principal Investigator. It should also be noted that when an amendment to the protocol substantially alters the study design or the potential risk to the patient, a revised consent form might be required.

The written amendment, and if required the amended consent form, must be sent to the IRB for approval prior to implementation.

12.4 Obligations of Investigators

The Principal Investigator is responsible for the conduct of the clinical trial at the site in accordance with the Code of Federal Regulations, Good Clinical Practice and/or the Declaration of Helsinki. The Principal Investigator is responsible for personally overseeing the treatment of all study patients. The Principal Investigator must assure that all study site personnel, including sub-investigators and other study staff members, adhere to the study protocol and all applicable regulations and guidelines regarding clinical trials both during and after study completion.

The Principal Investigator at each institution or site will be responsible for assuring that all the required data will be collected and entered onto the Case Report Forms. Periodically, monitoring visits will be conducted and the Principal Investigator will provide access to original records to permit verification of proper entry of data. At the completion of the study, all case report forms will be reviewed by the Principal Investigator and will require his/her final signature to verify the accuracy of the data.

13.0 Withdrawal of Subjects

Patients can be taken off the study at any time at their own request, or they may be withdrawn at the discretion of the investigator for safety, behavioral or administrative reasons. The reason(s) for discontinuation will be documented and may include:

- Patient voluntarily withdraws from treatment (follow-up permitted);
- Patient withdraws consent (termination of treatment and follow-up);
- During the mapping and ablation procedure, if the patient is not deemed sufficiently stable to perform the research mapping procedure;
- Patient is unable to comply with protocol requirements;
- Patient experiences toxicity that makes continuation in the protocol unsafe;

- Treating physician judges continuation on the study would not be in the patient's best interest;
- Lost to follow-up. Example language: If a research subject cannot be located to document survival after a period of 1 year, the subject may be considered "lost to follow-up." All attempts to contact the subject during the one years must be documented.

14.0 Risks to Subjects

The general risks related to participation in this study are predominantly those related to standard ablation therapy which the patient would be exposed to even if he/she proceeds with ablation without participating in this study. There is a risk of death with any serious complication related to ablation therapy that does not respond to emergency treatment.

This study involves the following risks related to the insertion or placement of catheters, the use of medications needed for the ablation procedure, moving the catheters in the heart, or delivery of energy inside of the heart.

The insertion of the catheters into the leg veins or arteries can be accompanied by the following:

- The possibility of infection, bleeding, bruising, pain or blood clot formation under the skin. A blood clot can develop in one of the veins in the leg or even in the lungs. A vein or artery could be injured and may require surgery for repair.
- Development of a bladder or kidney infection, infection elsewhere in the blood, pneumonia or fluid in the lung.
- The possibility of air entering the blood stream.

Medications given during the procedure can also have side effects:

- X-ray (Fluoroscopy) used to visualize the heart and veins may cause a skin rash. If dye is given, this can also damage the kidneys.
- The dye and anesthetic drug may produce an allergic response leading to a skin rash, a drop in blood pressure, or difficulty breathing. If this occurs, a ventilator will be used and the procedure can be continued. In rare cases, pneumonia could develop.
- The blood thinner, heparin, or similar drug could cause bleeding anywhere in the body.
- Nausea or a visual migraine-like headache.

Other procedure risks are related to positioning catheters within the heart:

- The most serious of these is heart muscle perforation by a catheter. In many cases the hole created by the catheter seals when the catheter is removed.
- In some cases, bleeding into the sac surrounding the heart could result in a drop in blood pressure. In such cases, a needle and catheter tube may be inserted from a position underneath the breastbone or between the ribs to drain this blood. In rare cases, open-chest surgery may be required.
- Moving the catheters within the heart could damage a heart valve, which could require surgical repair or replacement.
- A heart attack or stroke could also occur.

- An artery around the heart may spasm, develop a blood clot, or be damaged.
- There is also a possibility that the normal electrical system could be damaged, making a pacemaker necessary.
- The X-rays used to guide catheter placement could cause skin burns, or in the long run result in some form of cancer, or damage to the heart or lungs.
- Pacemaker leads could be disturbed or the pacemaker damaged, making repair or replacement necessary.

The final group of risks has to do with the actual ablation:

- Chest pain could be experienced when the energy is delivered, or inflammation around the heart may cause chest pain after the procedure.
- In addition, energy delivery on the left side of the heart could lead to blood clot formation, cause a stroke, or other organ damage.
- With energy delivery, there is also a slight increase in the chance of a heart attack, or the development of an atrial esophageal fistula. This can produce severe infection or a severe stroke, both of which may cause death.
- Ablation in or near a vein can also damage the vein itself.
- In a low percentage of cases, a pulmonary vein can be narrowed or significant scarring may occur, which can cause permanent lung damage. In some cases, an angioplasty (balloon) procedure may be required to open up this narrowing or scarring with a balloon catheter. In other cases, a coil or "stent" may be required to keep the vessel open. If the vessel re-narrows after the stent is placed, a repeat catheter procedure on more than one occasion could be required. Under rare circumstances open-heart or lung surgery could be required to correct the narrowing or scarring. In most cases, this can be dealt with successfully, although the consequences could be serious or cause death.
- There is a possibility of damage to one of the nerves around the heart. In rare cases, a nerve supplying the diaphragm (the muscle that helps with breathing) may become sufficiently damaged to cause the diaphragm to be paralyzed (unable to move). This is unlikely to be serious, and the muscle function usually returns over the course of 4 to 16 months, although sufficient damage could lead to permanent diaphragm paralysis.
- There may be elevated temperatures or abnormal blood tests.

It is possible that AF may return following the catheter ablation procedure requiring medication therapy, one or more additional ablations, or the rhythm may become worse. Overall, from the clinical portion of the ablation procedure, the risk of a serious complication is between 2-3%. The risk of a minor problem is approximately 5%.

The specific risks related to this study relate to the potential lengthening of the procedure due to additional mapping and the possibility that the sites identified by the EMR mapping for ablation do not lead to successful ablation of the AF.

Confidentiality: Patient confidentiality is an important issue in any clinical research study. All stored data will be de-identified using established protocols. Subject's names will not be used in publications or data analyses nor will they be available for discussion by any investigators other than the treating physicians.

15.0 Potential Benefits to Subjects

The possible benefits to the subjects from this study may include fewer or no more episodes of atrial fibrillation and reduction or elimination of AF-related medication. In cases where participation in this study does not improve AF and its symptoms, the information that is learned from this study may benefit other people with AF and may advance medical understanding of arrhythmias.

16.0 Vulnerable Populations

Not applicable, no vulnerable populations to be enrolled in this study.

17.0 Multi-Site Research

Not applicable, not a multi-site study.

18.0 Community-Based Participatory Research

Not applicable.

19.0 Sharing of Results with Subjects

The research subjects will not be given the results of the research. The subjects may be given results of their personal findings at the discretion of the treating Cardiac Electrophysiologist.

20.0 Setting

Subjects will be recruited at the University of Miami Hospital and the Cardiovascular Multispecialty Clinic. The ablation procedure and EMR recordings will be performed in the Cardiac Catheterization Lab at the University of Miami Hospital.

21.0 Resources Available

This study will involve the recruitment of up to fifteen (15) subjects with AF with one prior failed ablation. Patients undergoing a second catheter ablation procedure based on clinical guidelines (as determined by patient and his/her physician) will be considered for this study. Patients with persistent AF (as defined per the most recent guidelines) will be considered for this project. Subjects will be recruited from the medical center environment using standard techniques.

All of the critical facilities/resources needed for the success of this project are available to the PI and research staff. The PI is responsible for delegating study-related tasks to the appropriate personnel for the purposes of this study. Personnel, including sub-I's, and with oversight from the PI, are expected to abide by all laws, regulations, and policies enforced

by the aforementioned entities. All personnel involved in this study will have successfully completed institutional training for human-subjects protections (e.g. CITI Training).

22.0 Prior Approvals

Not applicable.

23.0 Recruitment Methods

Subjects undergoing a second ablation procedure will be recruited from patients at the University of Miami. Investigators and/or study coordinators will approach the patients, explain the protocol, and ascertain whether they would be interested in participating, and prospective subjects will be provided with a copy of the approved informed consent for review.

The research subjects will not be financially compensated for participation in the study.

24.0 Local Number of Subjects

Approximately fifteen (15) subjects will be enrolled in this study and screened for participation in this study. Ten (10) participants found eligible for the trial will receive the ablation procedure and then will be followed every 3-12 months, as clinically indicated, after completion of (or early withdrawal from) study treatment, for a minimum of one (1) year. These ten patients will be matched with a cohort of age and sex matched patients who have undergone a second AF ablation procedure for persistent AF with conventional methods.

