3.0 Inclusion and Exclusion Criteria

Approximately fifteen (15) subjects will be recruited from the University of Miami. Patients will be screened for participation in this study by the investigator or his clinical staff for inclusion. The study aims to complete ten (10) participants through the ablation procedure and a minimum of one (1) year follow-up.

INCLUSION CRITERIA:

- Male and female, at least 21 years of age
- Subjects with persistent AF with one prior failed ablation for persistent or long standing persistent AF

EXCLUSION CRITERIA:

- Inability to sign consent.
- Patients with a life expectancy <1 year.
- Patients with chronic kidney disease with sufficiently low GFR that precludes either CT angiogram of the heart or contrast MRI study.
- Patients with contraindications to catheter ablation for atrial fibrillation (i.e. left atrial thrombus, class IV heart failure, etc)
- Pregnant women and women that are breast feeding
- Patients with multiple (2 or more) prior failed ablations.
- Patients who have had chemotherapy or radiotherapy within 4 weeks prior to entering the study or those who have not recovered from adverse events due to agents administered more than 4 weeks earlier.

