will be remapped a second time to determine if another potential source still exists. If so, additional ablation will be performed at that site. After ablation based on the morphology recurrence plot, if AF has not terminated, *physician discretion will determine whether further EMR mapping guided ablation or further “standard” ablation will be performed as per physician protocol.* AF termination will be diagnosed if either sinus rhythm is restored with ablation or a regular atrial tachycardia or flutter ensues. Stable coronary sinus recordings will be used to assess ablation-induced slowing using the real-time software. The 3-D position of each ablation lesion will be documented.

10.0 **Data and Specimen Banking**

No biological specimens will be collected or stored for this research.

The data that will be stored includes demographic/clinical information on the research subject and the data from the EMR protocol. Please see section 11 for more information on the length of storage, location, access, etc. Any data requests from outside parties may also be submitted via written request to the PI and all data will be de-identified prior to release.

11.0 **Data Management**

Data Analysis

Clinical Data: Demographic and clinical data will be tabulated as means and standard deviations for continuous variables and counts with percentages for categorical variables.

For EMR Data: We will compare the cycle length prolongation seen with EMR ablation to that seen in a cohort of age and sex matched patients selected from our database of patients who have undergone a second AF ablation procedure for persistent AF with conventional methods. We will also compare acute termination rates and procedure duration. A difference of 10% in cycle length slowing between recurrence-based ablation vs. conventional ablation can be detected with 10 patients per group with 0.89 power. We will define a successful Phase I as AF termination or cycle length slowing of the coronary sinus of at least 15% in at least 7 of 10 patients from morphology recurrence mapping directed ablation.

Data Confidentiality

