29.0 Consent Process

Potential subjects will be identified by clinical physicians at the University of Miami and informed about the details and significance of this study. Investigators and/or study coordinators will approach the patients, explain the protocol, and ascertain whether they would be interested in participating, and prospective subjects will be provided with a copy of the approved informed consent for review. If a potential subject is interested in enrolling, informed consent and HIPAA authorization will be obtained from the subject by personnel involved in the study. Signed informed consent will be administered and HIPAA

authorization obtained either at the potential subject's clinic visit or prior to the ablation procedure.

Prospective subjects may speak languages other than English. Spanish-speaking subjects will be consented with a certified Spanish translation of the consent form. Prospective subjects who speak languages other than English or Spanish will be consented using a qualified translator to translate the English document and a translated short form of the consent in their own language.

A waiver of consent and waiver of HIPAA will be requested for matched historical control subjects. Patients in the historical control group will not undergo any research procedures; their standard of care clinical data will be used retrospectively as a comparison group to the research participants. The minimum necessary protected health information will be collected from the records of the matched historical control subjects. Only essential information will be taken from their medical records in order to ensure comparability with enrolled subjects; study team members will not contact these control subjects. The information will be stored in locked areas in the research offices of the Cardiovascular Division and password-protected computers; only personnel involved in the research will have access. Because these subjects will be historical controls and their information would be taken from medical records, it would be difficult to obtain consent and HIPAA authorizations from this group prior to reviewing their records.

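### The historical controls are not held to the trial's own requirement that the first ablation was for persistent or long-standing persistent AF, so the planned comparisons may be confounded by AF type at the first ablation

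*Combined protocol and SAP*

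**What the plan says.** **Trial patients.** The inclusion list in Section 3.0 reads "Subjects with persistent AF with one prior failed ablation for persistent or long standing persistent AF". The exclusion list removes "Patients with multiple (2 or more) prior failed ablations", so the prior ablation is the first one. AF type is thus fixed at two times: at entry and at the first ablation.

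**Controls.** Section 11.0 (Data Analysis) describes an age and sex matched cohort "selected from our database of patients who have undergone a second AF ablation procedure for persistent AF with conventional methods". Section 24.0 repeats this almost word for word; there the treated group is "matched with a cohort of age and sex matched patients who have undergone a second AF ablation procedure for persistent AF with conventional methods". AF type is fixed once, at the second procedure.

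**Comparability.** Section 29.0, on the consent waiver for controls, says "Only essential information will be taken from their medical records in order to ensure comparability with enrolled subjects". It names no criterion and no further matching variable.

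**Use of the controls.** Section 11.0 compares cycle length prolongation between the groups and adds "We will also compare acute termination rates and procedure duration". It states that a 10% difference in cycle length slowing "can be detected with 10 patients per group with 0.89 power".

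**The concern.** Eligibility should define the pool from which controls are drawn; matching then works inside that pool. Here the written rule for controls is wider than the rule for trial patients on one clinical feature, AF type at the first ablation. A control may match perfectly on age and sex and still be someone the trial would have turned away.

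It is plausible that this feature bears on the atrial substrate and on the lesions already present at the second procedure, although the documents do not discuss it. If it does affect slowing, termination or procedure time, a difference in case mix would be read as an effect of EMR guidance, or would hide one. Matching on age and sex cannot remove it. With ten controls, each control outside Section 3.0 is one tenth of the comparator.

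**Working it through.** **1. The two entry rules side by side**

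| Feature | Trial patients (Section 3.0) | Controls (Sections 11.0 and 24.0) |
|---|---|---|
| AF type at the second procedure | Persistent | Persistent |
| Number of prior ablations | One | One, since this is the second |
| Prior ablation failed | Stated | Not stated, but largely implied by a repeat procedure |
| AF type at the first ablation | Persistent or long-standing persistent | No condition |
| Age, sex | At least 21, either sex | Matched to trial patients |

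Only the fourth row is a material gap. The test case is a patient with a first ablation for paroxysmal AF, later progression, and a second ablation for persistent AF by conventional methods. That patient meets Sections 11.0 and 24.0 and fails Section 3.0.

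**2. The plan's own figure**

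The stated power of 0.89 cannot be reproduced directly, because Section 11.0 gives no standard deviation, test, alpha or sidedness. I take the 10% as 10 percentage points of slowing and assume alpha 0.05, 10 per group and an independent-samples t-test. Power 0.89 then needs a standardised difference of 1.508 (two-sided), so SD = 10 / 1.508 = 6.63 points. One-sided, it is 10 / 1.336 = 7.49 points. The figure is attainable, and the present point does not change it.

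**3. How ineligible controls would enter the result**

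Let f be the share of controls whose first ablation was for another AF type, and g the amount by which their mean slowing differs from that of eligible controls, whose mean is m.

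- Control mean = (1 − f) × m + f × (m + g) = m + f × g.
- Estimated EMR effect = true effect − f × g.

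If g is positive the EMR effect is understated; if negative, overstated. The documents give neither f nor g, so the values below are assumptions that show scale only. They use SD 6.5 (near 6.63; base power 0.902) and a two-sided t-test at 0.05, where the chance of a false positive in EMR's favour is 2.5% without bias.

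| f | Size of g (points) | Bias f × g (points) | False positive in EMR's favour, if bias favours EMR | Power at a true 10-point difference, if bias is against EMR |
|---|---|---|---|---|
| 0.1 | 2 | 0.2 | 2.9% | 0.890 |
| 0.3 | 5 | 1.5 | 7.1% | 0.790 |
| 0.5 | 5 | 2.5 | 12.6% | 0.685 |

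The effect runs from negligible to appreciable, in either direction.

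**4. What is untouched**

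The Phase I success rule in Section 11.0 (termination, or coronary sinus slowing of at least 15%, in at least 7 of 10) counts trial patients only. Section 8.0 lists no comparison with controls among the endpoints.

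**The case against.** The best reply is that the gap is brevity, not a different rule. A second ablation for persistent AF can loosely be read as a repeat of an ablation for persistent AF. The protocol is also loose elsewhere about its own patients: Section 21.0 speaks of "recruitment of up to fifteen (15) subjects with AF with one prior failed ablation" and does not repeat the first-ablation condition. Section 29.0 shows that comparability is intended. And this is an early feasibility study that promises only preliminary efficacy data.

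Part of this stands. The documents do not show that an ineligible control was or would be chosen, and the consequence is limited to a supporting comparison. But the control wording gives the indication for the second procedure only, whereas Section 3.0, the formal criteria list, states the first-ablation condition in so many words. Section 21.0 is a summary, and Section 29.0 states a purpose without a rule. Feasibility status does not remove the concern, because Section 11.0 plans a comparison with a stated power and these controls are its only comparator.

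A reader might go further and infer that the controls escape the Section 3.0 exclusions generally. The documents do not support much of that:

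- Class IV heart failure is listed as an example of a contraindication to catheter ablation, and every control underwent ablation.
- Low GFR is not an absolute bar even for trial patients, since Section 9.0 lets those below 30 ml/min either be excluded or have MRI without contrast.
- Failure of the first ablation is largely implied by a second one for persistent AF.

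**Conclusion.** The point holds for AF type at the first ablation. Followed as written, Sections 11.0 and 24.0 admit controls whom Section 3.0 would refuse, and all three planned comparisons may be confounded as a result. This is a specific fault in the selection rule, and it merits correction because the correction is cheap and serves the aim stated in Section 29.0.

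Its size cannot be fixed from the documents. Under the assumptions shown, the bias in slowing runs from 0.2 to 2.5 points against a planned difference of 10, that is 2% to 25% of it, and could be zero if no such control is selected.

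A reader might infer that the comparison is biased against EMR, on the thought that later-progressing patients slow or terminate more easily. Nothing in the documents gives that direction. Nor do they support a claim that the trial's success criterion is compromised.

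**What to change.** In Sections 11.0 and 24.0, define the control pool as patients in the database who would have met the Section 3.0 criteria at their second procedure, and state in particular that the first ablation was for persistent or long-standing persistent AF. Match on age and sex only within that pool.

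If the first-procedure indication is not on record, or the pool becomes too small, report AF type at the first ablation in both groups and state this as a limit on the comparison.

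The cost is new wording in two sections and a record check. The check would fall under the waiver that Section 29.0 says will be requested, so the first-procedure indication should be named among the data items. The documents do not say whether the database holds that item or how large the pool is. The restriction will shrink the pool by an unknown amount and may loosen the age match.
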